RESPONSE: Skin integrity scales, change in ocular surface staining rating, participant comfort and satisfaction rating, and change in visual acuity. Skin integrity will be analyzed by applying a likert-type rating system to a high-mag/high-resolution photo documented image of the subject's lid skin. The number of adverse events will also be reported, defined as incidents which require temporary or permanent suspension of the participant's involvement. These include any broken skin, decrease in visual acuity more than 2 lines, worsening of corneal rating of more than 1.5 points or other ocular surface ratings more than 2 points, and comfort rating lower than 5/10 (or 50cm on the 100cm visual analog scale).

7b). Secondary Outcome(s) - Secondary outcome(s) are measures of additional or less important research interest. They may include additional clinical, psychological, economic, or safety outcomes (e.g. treatment related side effects/adverse events). However, as these endpoints are not used to calculate study power and sample size it is often not possible to draw robust conclusions from the results.

RESPONSE: Video analysis of eyelid biomechanics to measure the completeness of eye closure and opening compared to 1) no device, 2) relative to the contralateral side (if normal), 3) relative to the ptosis crutch or external lid weights. The same paired comparisons will be performed for the clinician and participant rating scale data. 3) Cognitive score on the MoCA will be analyzed for relationship to length of time in the study and satisfaction rating scores).

STUDY PROCEDURES

8) In this section you need to clearly and comprehensively describe exactly what will happen to participants once they are enrolled in your study. Depending on the study it might include how potential participants will be approached, when they will be randomized, the frequency and duration of visits or whether they are expected to self-complete a daily diary at home, the duration of the study or follow-up, and any measurements taken at each visit (e.g. questionnaires, physical measurements, biological samples).

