RESPONSE: Twenty-five participants each with either paralytic ptosis or lagophthalmos will be enrolled for a total of 50 participants. The OCRO will assist in pre-identifying potential candidates targeting the practices of Dr.'s [name], [name], and [name]. They will mention the study to them/providing approved recruitment information (flyer and study description page). If OCRO pre-screening misses someone whom the Dr.'s think might be a candidate, they will mention the study and have their clinical staff provide the approved recruitment materials (a flyer and study brochure). A separate appointment will be arranged for the study candidate to return, if they are interested, to speak with the PI about the study and perform informed consent (conducted by the PI or other trained and experienced study personnel). Study visits may occur at MEEI in the Oculoplastics, Neuro-Ophthalmology, or Vision Rehabilitation Clinics, or at Schepens Eye Research Institute in the Lions Exam room booked with the online SERInet scheduling system. If seen at SERI, all data collected will be for research purposes (no clinical component); i.e. there will not be any overlap with their typical Ophthalmological care. If data is collected at MEEI, there may be, in the interest of efficiency, measurements taken clinically which can also be used for research to include visual acuity and slit lamp biomicroscopy. The PI will explain the study as detailed in the "consent" section and administer a pre-consent cognitive screening using the Mini-Mental State Exam (MMSE). If score is 18-23 (maximum of 30) representing mild cognitive impairment (Tombaugh et al 1992), candidates will be asked return with a caregiver (if one is not present). If score is <18, they will not be eligible. After the consent process, participants will complete the VFQ-25 (Mangione, 2001) and the MoCA (Montreal Cognitive Assessment, Nassreddine et. al 2012), have their visual acuity measured, anterior segment evaluation with NaFl and Lissamine Green, and a video recorded of their baseline eyelid function (capturing only the eyes).

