This will be followed by fitting of the experimental magnetic device. A video is recorded for approximately 1 minute to document device performance and a rating instrument (visual analog scale for participant measures and a likert-type 10-pt scale for the examiner) is administered to capture subjective comfort and opinion of efficacy (see rating scales attached). **DEVICE FITTING DETAILS-THE IMMEDIATE TRIAL: FOR PTOSIS**, In order to best fit the MLP we will measure 1) the force (i.e. magnet size) needed to elevate the paralyzed lid; 2) the thickness of the coating on the spectacle magnet needed to allow adequate blinking; 3) the best orientation of the magnets (thru height or thru thickness). Force measurement to open or close the eye lid may be taken by attaching a low force transducer (miniature strain gauge) to the lid(s) with a small piece of IV 3000 medical tape, a 2-3 minute procedure.

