Next, a lid attached magnet array (see photos in manuscript attached) is painlessly applied to the upper lid with the participant's eye closed by placing a small swatch of Tegaderm medical adhesive (3M, St. Paul MN, Smith and Nephew, Canton MA) over the top of the micro-magnet array (a 1-minute procedure). For ptosis the array is only attached to the upper lid and a set of fit-over frames with a larger magnet embedded within the upper eye wire (spectacle magnet), which can be worn over the participants own glasses if needed, will be placed on and adjusted to the appropriate position. This secondary spectacle mounted magnet activates the ptosis system, providing the force to lift the lid. The spectacle magnet must be encased in plastic, and if the coating is too thin, the patient will not be able to blink properly. To determine the best coating thickness we will test 10 different coating thicknesses, done with 1mm plastic inserts which can be stacked. The video is recorded and rating instruments completed. This process is then repeated for lid magnets having a slightly modified polarity (thru height compared to the standard thru thickness). We will also test 4 different orientations of the spectacle magnet to determine the best fitting. **FOR LAGOPHTHALMOS** (failure of eye closure, e.g. facial palsy) the participant will first be fitted with a predicate device, an external lid weight, applied with double-sided "blink-eze" adhesive (supplied by the distributor with the product) and the video recording and rating instruments completed. Then this will be removed and lid magnet arrays identical (or very similar) to those described for ptosis will be applied to the upper and lower lids. The weight of the upper magnet will pull the eyelid down in a similar manner as the gold lid weight. (Townsend, 1992) The magnet on the lower lid will promote a more complete blink as the two magnet arrays draw towards one-another. A secondary

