spectacle mounted magnet may also be used for lagophthalmos (mounted within the inferior eye-wire to pull the upper lid down). In this scenario there is no lower lid array. **20 MINUTE TRIAL:** For both the ptosis and lagophthalmos magnet devices: If experimenter likert-type scale score is greater than or equal to 6 on the blink mechanics and efficacy and better than 8 on the skin integrity and the participant rated comfort is greater than or equal to 5/10 on likert-type or 50mm or better on a 100mm Visual Analog Scale and they express a desire to continue wearing the device, they will be offered participation in an extended 20 minute trial. This is followed by a repeat of the visual acuity, slit lamp exam, video and rating scale data collection. **EXTENDED 1-WEEK TRIAL:** Participants who have a successful 20 minute magnet device trial defined as an Examiner Rating Scale score of greater than or equal to 6 on the blink mechanics and efficacy, better than 8 on the skin integrity, participant rated comfort greater than or equal to 5/10 (or 50mm on a 100mm Visual Analog Scale), and express a desire to continue wearing the device will be offered participation in an extended 1-week trial. These cut-offs were based on observations during the pilot study at Spaulding (see manuscript attached) where patients who reported a desire to wear the device typically rated their comfort and satisfaction at this level or better. The PI or other trained study staff supervised by the PI will train the patient how to apply and remove the lid magnet; similar to what is done for insertion removal of contact lenses. They will be trained how to place on the secondary magnet spectacles to sit in the correct position on their face. If the participant is able to successfully demonstrate the ability to do this, only then will the magnet device be dispensed home with the patient (see exception* below). During each 1-week during the extended trial, the participant will be advised (instructional sheet sent with the participant) to wear the device as much as they would like up to 8 hours per day in the case of ptosis and 24 hours per day for lagophthalmos so long as comfort remains 5 or better (see participant instructions). Participants will be asked to document their wear time and assess their comfort on a 10-pt scale (10 being best) on a regular (min. daily) basis. For lagophthalmos, the device ideally will be worn 24 hours/day. For ptosis, the magnet glasses will be removed at night, and the lid magnet will remain attached to the eyelid. The participant may shower/wash face with the lid magnet on as the Tegaderm is not critically bothered by water and the magnet is encased in PDMS. They will be advised not to submerge the device (i.e. swim with the device on). Lid magnets will be removed and applied as they start to become detached (typically 2-3 days). If self-assessed comfort is worse than 5/10 or if the intervention fails (eg. stops working or falls off and cannot be reapplied) the participant will be instructed to contact the PI directly. The PI will advise if the device should be removed, and will come to MEEI or Schepens within 24 hours of the complication to evaluate the problem. If there is a problem requiring immediate attention, the participant will be advised to seek attention in the MEEI EW. **AT A 1-WEEK FOLLOW-UP** study appointment we will repeat visual acuity, slit lamp, rating instruments and video recording. **SAFETY CUTOFFS:** The participant's study status will change to suspended and an adverse event reported to the IRB with any of the following findings at the follow-up or any emergency visit: Any broken skin, decrease in visual acuity more than 2 lines, worsening of corneal rating of more than 1.5 points or other ocular surface ratings more than 2 points, and comfort rating lower than 5/10 (or 50cm on the 100cm visual analog scale). The extended trial of the magnet device may be renewed 3 times (for a total of 1 month with weekly visits) as long as the above mentioned criteria continue to be met. If still safe/effective at 1 month, the participant will be given the option to take the device home for an additional 1 month. The device trial/study ends after 8-weeks (4 weekly trials followed by a 1-month trial) or with failure/complication or voluntary withdrawal. If the device is successful over the duration of the study and the participant would like to continue wearing it, a clinical decision will be made as to if and for how long per day it should be worn. This is justified when there appears to be no other equivalent treatments which may be substituted. It would not be ethical to retract the device from a participant if it is working and there is no other comparable option. In such cases, the participant will return 1 month later for an additional follow-up evaluation prior to turning the maintenance of their care over to the neuro-ophthalmology, oculoplastics, or vision rehabilitation service. Their specialist will continue to monitor for complications after the study if the patient keeps the device. The study will end when 25 participants in each group have completed the study (~2yrs). **EXCEPTION* TO TRAINING REQUIREMENT:** If the participant is unable to apply and remove the device themselves (physical or cognitive limitations) and/or they have cognitive impairment (MMSE 20-23), they may still participate in an extended 1-week trial if the following criteria are met: 1) a caregiver is able to be trained to apply/remove the device, 2) The primary caregiver assures 24-hour supervision (see form on the last page of the "instructions for use document"), 3) The cognitively impaired participant (or participant who cannot apply the device themselves) agrees to attend daily study visits for the first

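### Section 7b extends three paired comparisons to the comfort, efficacy and blink ratings, but section 8 describes no rating without a device or of the fellow eye and, in ptosis, none with the crutch

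*Combined protocol and SAP*

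**What the plan says.** Section 7b plans video analysis of how completely the lids open and close, "compared to 1) no device, 2) relative to the contralateral side (if normal), 3) relative to the ptosis crutch or external lid weights". The next sentence carries these references over to the subjective data: "The same paired comparisons will be performed for the clinician and participant rating scale data".

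Section 8 gives the order of measurement. After consent, participants complete the VFQ-25 and the MoCA, then "have their visual acuity measured, anterior segment evaluation with NaFl and Lissamine Green, and a video recorded of their baseline eyelid function". Next comes the device: "This will be followed by fitting of the experimental magnetic device". The ratings first appear at that step: "A video is recorded for approximately 1 minute to document device performance and a rating instrument" "is administered to capture subjective comfort and opinion of efficacy (see rating scales attached". In lagophthalmos the lid weight is fitted and rated before the magnet. After the 20-minute trial the schedule reads: "This is followed by a repeat of the visual acuity, slit lamp exam, video and rating scale data collection". The ratings are repeated at the 1-week follow-up.

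**The concern.** A paired comparison needs two values from the same person. If section 8 is followed exactly, the comfort, satisfaction, efficacy and blink-mechanics ratings exist only with a device on or after it has been worn. An analysis that the plan commits to would then have no data on one side.

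The timing matters because the two kinds of rating differ in whether they can be recovered. An examiner could score blink mechanics later from stored video. A participant's comfort before fitting cannot be obtained once the device has been fitted. If nobody notices until analysis, the participant side of the no-device comparison is lost for everyone already fitted.

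**Working it through.** The plan gives no figure for this point, so the check traces each reference in 7b to the step in section 8 that would supply it.

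**Inputs**
- References: no device; fellow eye if normal; crutch or lid weight (7b).
- Ratings concerned: participant comfort and satisfaction, participant and examiner opinion of efficacy, examiner blink mechanics (sections 7a, 8 and 10).
- Planned size: 25 ptosis and 25 lagophthalmos, 50 in total (section 8).

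**Trace for these ratings**

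| Second value needed | Ptosis | Lagophthalmos |
|---|---|---|
| No device | none described | none described |
| Normal fellow eye | none described | none described |
| Comparator device | no crutch fitting or rating described | lid weight rated at fitting |

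Three references in two groups make 3 × 2 = 6 comparisons. Those without a described second value number 2 (no device) + 2 (fellow eye) + 1 (crutch in ptosis) = 5, which leaves 6 − 5 = 1. That one is magnet against lid weight, in the group that makes up 25/50 = 50% of the planned sample. Its time-matched pair is the immediate fit, because section 8 describes a lid-weight rating only then.

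**The same trace for other measures**
- Lid video: a baseline recording exists, so the no-device comparison is supported.
- Ocular surface staining: the stained exam precedes fitting and 7a analyses change, so the no-device comparison is supported.
- VFQ-25: it is taken before fitting, but it is a different instrument and section 8 lists no repeat.

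**The crutch elsewhere in the plan.** Section 10 lists magnet-versus-crutch comparisons among the research procedures. Section 13 estimates 10 participants for the ptosis between-device comparison, citing 7 pilot participants with p=0.05 for comfort and p=0.08 for opening. Alpha, sidedness and power are not stated. Assuming two-sided p-values, a two-sided alpha of 0.05 and 80% power, comfort gives dz = t/√n = 2.447/√7 = 0.925 and n = ((1.960 + 0.842)/0.925)² = 9.2, so 10; an exact paired t calculation gives 12. Opening gives dz = 2.104/√7 = 0.795 and n = 13 or 15. The 10 can therefore be reached from comfort under these assumptions. It says nothing about the no-device or fellow-eye comparisons. It does show that a crutch comparison is intended, although the ptosis fitting steps in section 8 never mention a crutch.

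**The case against.** **The forms are not available.** The rating scales and recording forms are attachments and might hold baseline or fellow-eye items. This stands as a limit on the wording. A reader might infer that the comparisons are impossible to derive, but the documents support only that the described procedures do not supply them. Even a suitable form would need a place in section 8 before fitting.

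**Some ratings do have a pre-device value.** A reader might infer that every rating is taken with a device on, or that 0 of 50 participants would have data. Neither holds. Ocular surface staining is a clinician rating with a baseline exam. The fellow-eye comparison applies only where that eye is normal, so 50 is not its denominator. Section 12 also plans later rating from photos or video, though only of skin integrity.

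**The 7b sentence may be broader than intended.** Section 10 ties the no-device reference to the video, and section 14 names paired t-tests only for opening and closing. That is a fair reading, but 7b as written says otherwise, so the text needs changing either way.

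**The hypotheses survive.** This stands. Hypothesis 4b(a) rests on image analysis, for which baseline video exists. Hypothesis 4b(b) sets an absolute mean comfort of at least 6/10 and needs no untreated value.

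**Bias towards the magnet.** A reader might infer that the lid weight's immediate rating will be paired with later magnet ratings, which come only from people who passed the score thresholds. The plan does not state that pairing, and an immediate-fit pair exists. The direction is not settled either: selection could raise later ratings and longer wear could lower them. What remains is that 7b does not name the time point.

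**Conclusion.** The concern holds for the comfort, satisfaction, efficacy and blink-mechanics ratings. The described data collection does not support their no-device and contralateral comparisons in either group, and it supports the device-versus-device comparison only in lagophthalmos. One of six comparisons has both values described.

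This assumes that section 8 is the complete schedule and that the attached forms add no baseline or fellow-eye ratings. A secondary analysis is affected. The primary safety and feasibility question, the video comparison with no device and the staining results are not. The change should be made before enrolment, because participants' pre-fit comfort cannot be recovered afterwards.

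**What to change.** 1. In section 8, before any device is fitted, add the participant's eye-comfort item and an examiner blink-mechanics score for the affected eye.
2. Where the fellow eye is normal, score its blink mechanics from the baseline video already recorded, after confirming that the recording shows both eyes.
3. In 7b, limit the no-device and contralateral rating comparisons to those items. Satisfaction with a device has no meaning when none is worn.
4. In 7b, state that device-versus-device rating comparisons use the immediate-fit ratings of everyone fitted with both devices.
5. Reconcile the crutch comparison in 7b, and the matching text in sections 10 and 13, with the ptosis procedures in section 8, which describe no crutch.

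The cost is a few minutes at the baseline visit with existing forms and staff, a small extra burden for participants, and some rewording. If the sponsor prefers no new ratings, limiting the 7b sentence to device-versus-device comparisons removes the inconsistency, but it gives up the no-device and fellow-eye rating comparisons. Item 5 is needed in either case.

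### Relating MoCA to length of time in the study would mix the protocol's cognition-linked home-use rules with feasibility

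*Combined protocol and SAP*

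**What the plan says.** All references are to the combined protocol and SAP.

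- **Section 7b (secondary outcomes):** "Cognitive score on the MoCA will be analyzed for relationship to length of time in the study and satisfaction rating scores". No test, time origin or treatment of participants who finish is given.
- **Section 8, screening:** the MMSE comes before consent. On the lower limit: "If score is <18, they will not be eligible". For MMSE 18-23, "candidates will be asked return with a caregiver (if one is not present").
- **Section 8, baseline:** "After the consent process, participants will complete the VFQ-25 (Mangione, 2001) and the MoCA". MoCA is therefore scored before device fitting, the 20-minute trial and the decision on home use.
- **Section 8, home use:** the participant must first show that they can apply and remove the device, and "only then will the magnet device be dispensed home with the patient".
- **Section 8, exception to the training requirement:** for participants who cannot apply the device, "and/or" being the link to cognition, the text continues "they have cognitive impairment (MMSE 20-23), they may still participate in an extended 1-week trial if the following criteria are met". The criteria are a trained caregiver, supervision ("The primary caregiver assures 24-hour supervision") and daily study visits in the first week of the extended trial.
- **Section 8, end of trial:** "The device trial/study ends after 8-weeks (4 weekly trials followed by a 1-month trial) or with failure/complication or voluntary withdrawal". Participants who keep the device have one further evaluation a month later.
- **Section 13:** feasibility is reported as the proportions with a safety issue and completing the trial. MoCA is not mentioned.
- **Section 14:** descriptive statistics, repeated-measures ANOVA and paired t-tests. None is assigned to MoCA, and nothing is said about the 8-week limit or the caregiver route.

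**The concern.** Length of time in the study is partly an outcome and partly a product of the rules, and the rules depend on cognition, which is the explanatory variable. Two mechanisms act in opposite directions:

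- **Blocking.** A consented participant who falls under the exception but cannot meet its conditions has a low MoCA score on file and close to zero time. This says nothing about how that person would have coped at home. It pushes the association upwards (lower MoCA, shorter time).
- **Support.** A participant who meets the conditions has a trained helper, continuous supervision and more frequent examinations. If this helps retention, it pushes the association downwards. If the extra visits are a burden, it pushes it upwards.

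This is the only planned analysis of whether cognition matters, in what Section 1 describes as the first study to send participants home with the device. A spurious association would suggest that people with lower scores cannot manage. A masked one would suggest that they manage as well as others, when they did so with help that others did not have.

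**Working it through.** **1. The plan's own figure.** One week plus 3 renewals is 4 weekly trials. Adding 1 month (about 4 weeks) gives 8 weeks, as stated. No sample size, power or effect size is given for the MoCA analysis.

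**2. Order of events.** MMSE, caregiver request if 18-23, consent, MoCA, fitting, 20-minute trial, training or exception route, home use. MoCA precedes the home-use gate, so a participant stopped there has a score and can enter the analysis. The caregiver request precedes consent, so many candidates without a caregiver would never get a MoCA score. The group blocked after MoCA is what remains: caregivers who cannot be trained or cannot assure supervision, and participants who decline daily visits.

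**3. Blocking only, no true effect of cognition on retention.** From the documents: n = 50 and the 8-week limit. Assumed: MoCA-MMSE correlation 0.7; exponential time to stopping with rate -ln(0.6)/8 per week, so that 60% reach 8 weeks; time set to 0 for blocked participants; 15% or 30% of the source population below MMSE 24, with the lowest quarter of these excluded at entry. Among those enrolled, the impaired share is then (0.15 - 0.0375)/(1 - 0.0375) = 11.7%, about 6 of 50, or (0.30 - 0.075)/(1 - 0.075) = 24.3%, about 12 of 50. Spearman test at two-sided 5%, 4,000 simulated studies per setting:

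| Blocked among impaired | 15% below cut: mean r, significant | 30% below cut: mean r, significant |
|---|---|---|
| None (8-week limit only) | not run | 0.00, 5% |
| 10% | +0.03, 6% | +0.04, 7% |
| 25% | +0.06, 7% | +0.09, 11% |
| 50% | +0.12, 14% | +0.18, 25% |
| 75% | +0.17, 23% | +0.27, 48% |

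**4. Sensitivity to the assumptions**, again with n = 50 and no true effect:

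- 20-30% of enrolled participants impaired, 20-60% of them blocked, correlation 0.7, 60-80% completing: 9% to 57% significant.
- 10% impaired, with 10-20% of them blocked: about 5% to 9%.
- 20-30% impaired and 20-60% blocked, but MoCA drawn by MMSE band so that the two are almost fully separated, 80% completing: about 15% to 85%.
- Nobody blocked: 4% to 6%.
- Analysis restricted to participants dispensed the device: 4% to 6%, even with 60% of impaired participants blocked.

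**5. Support only, no true effect** (settings of step 3, 30% below the cut, nobody blocked). If support cuts the stopping rate of impaired participants to 0.5 or 0.25 of its value, mean r is -0.07 or -0.11, with 7% or 13% significant. If the added burden doubles their stopping rate, mean r is +0.09, with 10% significant.

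**6. A true effect** (stopping hazard multiplied by 1.5 per SD lower MoCA). Without limit or entry exclusion, mean r is about 0.32. With both, it is 0.26, 0.22 or 0.16 when about 40%, 60% or 80% reach 8 weeks. Adding support that halves the stopping rate of impaired participants gives 0.16 or 0.14 (40% or 60%). Support that cuts it to a quarter gives 0.06 to 0.08.

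**7. Information available.** The correlation detectable with 80% power at n = 50 is tanh[(1.960 + 0.842)/sqrt(50 - 3)] = tanh(0.409) = 0.39. If 80% complete, there are 50 x 0.20 = 10 discontinuations.

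**The case against.** The strongest reply is that Section 7b names no correlation and no raw time. A time-to-event analysis with completers censored would fit its wording, so the gap might be only an unspecified method. This stands in part, but censoring alone does not help: a participant refused home use under the exception would still count as a very early exit unless the time origin and the analysis set are defined.

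A second reply is that the caregiver request before consent removes many of the candidates who would later be blocked, and that the impaired and blocked shares in the simulations have no basis in the documents. This stands. It favours the low end of the range, and the 85% figure should not be taken as representative.

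Two stronger readings are tempting and are not supported. A reader might infer that the result would reflect only the rules and not feasibility. But time also ends through device failure, complication and voluntary withdrawal, which are genuine feasibility events, and the clinic-trial cut-offs apply to everyone. The result would be a mixture. A reader might also infer that the 8-week end produces a false association. It does not: with the limit alone, mean r is 0.00 with 5% significant. It censors those who last that long and weakens a true relation.

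It is also fair to say that MoCA appears in no hypothesis in Section 4, and that Section 13 reports feasibility without it.

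**Conclusion.** The concern holds in a limited form. As written, the variable mixes rule-driven exits and rule-driven support with real coping, and nothing in Section 14 separates them. The direction of bias cannot be known in advance.

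With no true effect and 50 participants, the false-positive rate ranges from about 5-6% (few impaired or few blocked) to about 50-60% (up to 30% impaired and most of them blocked, MoCA-MMSE correlation 0.7). About 85% needs near-complete separation of MoCA by MMSE band. The impaired share, blocked share, MoCA-MMSE correlation and completion rate are all assumptions.

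The analysis should be corrected, but the matter is secondary: the primary safety and completion summaries are unaffected. The satisfaction half of the sentence in Section 7b was not examined.

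**What to change.** In Sections 7b and 14:

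1. Label the MoCA analysis exploratory.
2. Among participants dispensed the device, relate MoCA to completion of 8 weeks (yes/no). If there are enough discontinuations, use time from dispensing to discontinuation, with completers censored at 8 weeks.
3. Tabulate participants never dispensed the device by reason and MoCA, keeping apart unmet caregiver, supervision or visit conditions, inability to apply the device, and failed clinic trials.
4. Report the exception route descriptively. A Cox model stratified by it is not workable on about 10 events, and the route also admits people with purely physical limitations.

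Separately, reconcile the MMSE bands in Section 8: the caregiver request covers 18-23, but the exception to the training requirement covers 20-23, so the route for scores of 18-19 is unclear.

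Cost: analysis wording and one reason-for-ending code, which should be recorded prospectively. The analysis loses the never-dispensed participants, and its result applies only to those dispensed the device. It removes the blocking artefact but not the effect of support, so any result describes retention under the help that the protocol provides.
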